#### 4.1.3 Planned adjustment for stratification

Because stratification will be used to ensure that at each surgical site there are equal numbers of patients in each group, the Cochran-Mantel-Haenszel (CMH) test will be used to generate an estimate of the association between implant type (H1 or THA) and achievement of CCS (achievement or not) while taking into account the possible confounding variable of surgical site. The data will be stratified into 4 levels for the 4 sites to create a series of 2x2 tables showing the association between implant type and CCS for each site and a weighted average of the odds ratios. The CMH test statistic will be calculated and p-value determined, with the null hypothesis being that all the odds ratios are equal to 1. Following this test, Woolf's heterogeneity test will be used to test the null hypothesis that all the odds ratios are equal to each other (even if they are not all equal to 1).

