## 2.2 Study objectives

The primary objective of this trial is to determine whether the H1 Implant is non-inferior to cementless THR in terms of CCS.

The key secondary objective is to determine whether the H1 Implant is superior compared to cementless THR in terms of physical activity and patient report outcome measures (PROMs).

Other secondary objectives are to compare the H1 Implant and cementless THR with respect to:

- Safety, through collection of all procedure and device related adverse events
- Noise generation, through patient survey.

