## 3.2 Randomisation and blinding

Randomisation will be performed using variable block randomisation with block sizes of 4, 6 and 8, with a 1:1 allocation to the 2 groups, with stratification across sites. This will ensure approximately equal numbers across groups and approximately the same number per group at each site (to control for differences in the trial population because of environmental, social and demographic factors), while allowing different total numbers at each site. It will also ensure that at any given time, the numbers in each group will be approximately equal, allowing the interim analyses to take place. The randomisation will be managed by the CRO via an electronic data capture (EDC) system, which uses a validated randomisation algorithm (Castor EDC). Once a patient has been consented, they will be assigned to a treatment group according to the pre-determined order inside the block. Stratification by site is recommended for multi-centre studies. The patients, clinical assessors and data analysts will be blinded to the intervention each patient has received for the 24 month post-operative period. The surgeon, operating theatre team, radiographic analysts and CRO cannot be blinded but will not be involved in the care of the patient after the intervention unless the patient requires revision surgery.

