## 3.3 Sample size

The sample size was calculated on the basis of the research hypothesis. Using pilot data from two sources, the CCS rates for cementless THR and the H1 Implant were estimated to be 91%3\* and 92.7%, respectively. With a non-inferiority margin of 8% and setting the probability of a type I error to 5% and power to 80% and using the following formula:

$$n = \left(\frac{z_{1-\alpha} + z_{1-\beta}}{P_{H1} - P_{THR} - \delta}\right)^2 \left(P_{H1}(1 - P_{H1}) + P_{THR}(1 - P_{THR})\right)$$

where:

n = required sample size  $P_{H1}$  = probability of success for H1  $P_{THR}$  = probability of success for THR  $\alpha$  = probability of a type I error  $\beta$  = probability of a type II error  $\delta$  = non-inferiority margin

<sup>\*This CCS for the cementless total hip was calculated from the publication referenced, but excluded intra-operative ceramic liner fractures because these have been practically eliminated with modern day ceramic (BIOLOX®*delta*) and do not occur with polyethylene cups. The control in the RCT will be cementless BIOLOX®*delta*-on-BIOLOX®*delta* or cementless BIOLOX®*delta*-on-PE THRs.

z = is the cumulative distribution function of a standardised normal deviate

The required sample size is 93 per group. Allowing for drop-outs, this gives a sample size of 100 per treatment arm, therefore a total of 200 patients will be recruited to the study. Assuming the cementless THR group goes on to match this pilot data of 91% success, 90% of H1 patients would be required to demonstrate composite clinical success to be non-inferior to the THR patients, with the margin of 8%.

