## 6.2 Analysis methods

Analysis methods for primary and secondary outcomes and subgroup analyses are summarised in Table 1. Outcomes shall be reported for each treatment group. No adjustments will be made for baseline variables. Categorical data will be summarised by numbers and percentages and 95% confidence intervals.

Continuous data will be summarised by mean, standard deviate and range if data are normal and by median, interquartile range and range of data are non-normal.

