#### Table 1. Summary of outcomes and analysis methods

Variable/outcome	Hypothesis	Outcome measure	Method of analysis
Primary: CCS	H1 Implant is non- inferior to THR	% patients achieving CCS	Blackwelder's non- inferiority test
Secondary: physical activity	H1 Implant is significantly better than THR	Average daily minutes of activity and mean bouted daily MVPA, minutes	Student's t-test (normal, equal variance) or Welch's t-test (normal, unequal variance) or Wilcoxon Rank-Sum (non-normal)
Secondary: physical performance assessment	H1 Implant is significantly better than THR	Number of chair stands in 30 seconds Time to perform stair climb test	
Secondary: HOS	H1 Implant is significantly better than THR	HOS Questionnaire	
Secondary: UCLA Activity Score	H1 Implant is significantly better than THR	UCLA Activity Score	
Secondary: safety	N/A	Adverse events and adverse device effects	N/A
Secondary: noise	N/A	Noise questionnaire	N/A
Adjustment for stratification	Odds ratios are equal across sites	% patients achieving CCS	Cochran-Mantel- Haenszel test followed by Woolf's heterogeneity test
Subgroup analysis: Low v High pre-op activity/physical assessment score/UCLA	N/A	Average daily CPM Mean bouted daily MVPA, minutes	Student's t-test or Welch's t-test or Wilcoxon Rank-Sum
Subgroup analysis: Low vs high "historical UCLA" score	-		
Subgroup analysis: male v female	N/A	% patients achieving CCS	Fisher's exact test
Subgroup analysis: small H1 Implants v all THRs	-		
Subgroup analysis: large H1 Implants v all THRs			
Subgroup analysis: H1 Implants v device type in the THR group			
Subgroup analysis: H1 Implants v bearing type in the THR group			

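### Randomisation is stratified by site, but the SAP plans no site-adjusted result that can be read against the 8-point non-inferiority margin

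*SAP*

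**What the plan says.** SAP Section 3.2 randomises "with a 1:1 allocation to the 2 groups, with stratification across sites" and gives control of population differences between sites as a reason.

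Section 2.2 sets the question: "The primary objective of this trial is to determine whether the H1 Implant is non-inferior to cementless THR in terms of CCS". Section 3.3 puts the margin at 8 percentage points on the difference in success rates, with 91% assumed for THR and 92.7% for H1.

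Table 1 gives the method for the primary outcome as "Blackwelder's non- inferiority test", with no stratified version. Section 6.2 adds: "No adjustments will be made for baseline variables".

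Site appears only in Section 4.1.3, headed as the planned adjustment for stratification. "The data will be stratified into 4 levels for the 4 sites to create a series of 2x2 tables", from which a weighted odds ratio is formed. Then: "The CMH test statistic will be calculated and p-value determined, with the null hypothesis being that all the odds ratios are equal to 1". After that, "Woolf's heterogeneity test will be used to test the null hypothesis that all the odds ratios are equal to each other".

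Table 1 lists the CMH and Woolf analyses in a row of their own. The hypothesis in that row is that the site odds ratios agree with one another. That is Woolf's null, not the CMH null of Section 4.1.3.

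**The concern.** A factor used to stratify randomisation would normally enter the primary analysis, or at least a supporting analysis of the same estimand. Here the site-adjusted analysis answers a different question on a different scale. The SAP gives no margin for the odds ratio and does not say what part the CMH result plays in the conclusion.

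At stake is whether the report can say that H1 is, or is not, non-inferior by 8 points after allowing for site. As planned it cannot. If the adjusted odds ratio and the unadjusted risk difference appear to disagree, no rule says which to follow or how to compare them.

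**Working it through.** **1. Is the planned primary test unstratified?** Section 3.3 says that with THR at 91%, H1 needs 90% success. Inputs: 100 per arm, margin 0.08, one-sided 5% (critical value 1.645), unpooled variance, no site term.

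- H1 at 90%: (0.90 - 0.91 + 0.08) / sqrt((0.0900 + 0.0819)/100) = 0.070/0.0415 = 1.69, which passes.
- H1 at 89%: (0.89 - 0.91 + 0.08) / sqrt((0.0979 + 0.0819)/100) = 0.060/0.0424 = 1.41, which fails.

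The 90% figure reproduces, which supports reading the test as an unstratified risk difference. (The 93 per group in the same section does not reproduce: the stated formula gives 98.3, so 99. That is a separate matter and does not bear on this point.)

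**2. Where does the margin lie on the odds-ratio scale?**

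- At the margin, 83% v 91%: (0.83/0.17)/(0.91/0.09) = 0.48.
- At the design rates, 92.7% v 91%: (0.927/0.073)/(0.91/0.09) = 1.26.

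An odds ratio of 1 is neither of these. A test of that null behaves as follows with 100 per arm, two-sided 5%:

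- H1 truly 8 points worse: power = Phi(0.08/sqrt((0.0819 + 0.1411)/100) - 1.96) = Phi(-0.27) = 39.5%, so about 60% of such trials are non-significant.
- Design rates: power is about 6% analytically and about 7% for CMH by simulation.

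So neither a significant nor a non-significant CMH result settles the margin question.

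**3. What does leaving site out cost?** Simulation, 200,000 trials per row, 4 sites of 25 per arm, one-sided 5% against -8 points. The stratified test weights the site differences by site size, which with equal arms is Mantel-Haenszel weighting. Site rates are assumptions, because the SAP gives none.

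| THR success by site | Type I error, unstratified | Type I error, stratified | Power, unstratified | Power, stratified |
|---|---|---|---|---|
| 91% at all four | 5.5% | 5.5% | 81.5% | 81.3% |
| 97, 93, 89, 85% | 5.2% | 5.4% | 82.0% | 82.2% |
| 99, 96, 89, 80% | 5.1% | 5.5% | 80.6% | 81.6% |

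Type I error is at a true difference of -8 points at every site. Power is at +1.7 points, except that in the last row the best site is capped at 99.9%. With equal arms within each site the two point estimates are identical. A further simulation with the same layout and assumed site rates put both methods at about 5.1-5.9% type I error and 81-84% power.

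**4. Can Woolf's test be computed?** It needs a log odds ratio from every site, which is undefined if a site-arm has no failures. With 25 per site-arm, equal sites and the design rates:

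- No failures in a THR cell: 0.91^25 = 0.095. In an H1 cell: 0.927^25 = 0.150.
- At least one empty cell among 8: 1 - [(1 - 0.095)(1 - 0.150)]^4 = 65%.

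With 23 per cell it is 71%. The SAP states no rule for empty cells.

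**5. Is test size a site matter?** The exact one-sided size of the unstratified unpooled (Wald) test at 100 per arm is 5.4% at 91% v 83%. At control rates not in the SAP, it is 6.3% at 95% v 87% and 7.1% at 97% v 89%. A Mantel-Haenszel-weighted difference with the same kind of variance, simulated with common site rates, gives 5.5-5.8%, 6.2-6.4% and 7.0-7.2%. The excess comes from the variance, not from omitting site. A score test (Farrington-Manning) gives 4.8%, 4.7% and 4.4%. Its exact power at the design rates is 78.0%, against 81.6% for Wald: a cost of 3.6 points.

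**The case against.** The strongest reply is that nothing practical changes. With balanced allocation within sites the estimate is the same with or without site, and the table shows operating characteristics that barely move. Under strong site differences the unstratified test is, if anything, slightly closer to 5%. This stands, and it limits the weight of the point.

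Second, site is not ignored: CMH supplies a site-weighted odds ratio, and Table 1 keeps it apart from the primary row. This also stands. A null of no difference would be the wrong null only if CMH were the non-inferiority test, and the SAP does not make it so.

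A reader might infer from step 2 that the trial has a 60% chance of endorsing an implant that is worse by the whole margin. The SAP does not support that. No section treats a non-significant CMH result as evidence of non-inferiority. The primary test decides, and it passes about 5% of the time in that case. A reader might also attribute the size excess in step 5 to the missing site term, and step 5 shows that this is wrong.

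Third, a conventional 0.5 correction makes Woolf's test computable, and the test is only supportive. That is fair. What remains is an unstated convention that will probably be needed.

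None of this supplies a site-adjusted result on the margin's scale, or a statement of the role of CMH.

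**Conclusion.** The point holds as a gap in specification. Site governs the randomisation, the primary test does not use it, and the analysis offered as the adjustment cannot be compared with 8 percentage points. The Table 1 row adds to the confusion by giving Woolf's null for both tests.

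The size is small: under 1 point of type I error and about 1 point of power. This rests on four equal sites of 25 per arm, equal arms within sites, and assumed site rates. Section 3.2 allows sites to differ in size, so these figures are indicative. The 65% chance of an empty cell rests on equal sites and the design rates, and concerns a supportive test only. The reason to act is consistency between design, analysis and margin at almost no cost. The primary conclusion is not in danger on this account.

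**What to change.** - **Primary analysis.** In Table 1 and Section 4.1.3, analyse CCS as a site-stratified risk difference, H1 minus THR, by stratified Miettinen-Nurminen or with Mantel-Haenszel weights. Conclude non-inferiority if the lower confidence limit, at the level the SAP fixes for the final test, lies above -8 points. Keep unstratified Blackwelder as a sensitivity analysis.
- **Section 6.2.** Except site from the statement that no baseline adjustment is made.
- **CMH and homogeneity test.** State that both are supportive and play no part in the non-inferiority conclusion. Correct the hypothesis in their Table 1 row.
- **Heterogeneity.** Present site-specific risk differences with intervals. If Woolf's test is kept, state the correction for empty cells. Breslow-Day or Tarone would avoid the per-site log odds ratio but stays on the odds-ratio scale.

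The cost is SAP wording and a few lines of code, settled before unblinding. The sample size need not change for the stratification itself. Mantel-Haenszel weights with an unpooled variance change power by about 1 point or less but leave the size excess in place. A score-type method removes it at about 3.6 points of power, a figure from the unstratified comparison that is assumed to carry over to the stratified form. That choice is separate from the use of site and should be made openly.

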#### 4.1.4 Confidence intervals to be reported

All confidence intervals presented will be 95% and two-sided.

#### 4.2 Adherence and protocol deviations

#### 4.2.1 Definition of adherence to the intervention and how it will be presented

Compliance will be assessed based on the % of patients who have attended all follow-up visits, completed the required questionnaires and assessments, and worn the activity tracker for the requested amount of time. Individual % compliance figures shall be calculated for each type of activity at each time point. Descriptive statistics on the percent compliance (N, mean, SD, median, minimum, maximum) will be summarised by randomisation group, time-point and type of activity.

#### 4.2.2 Definition of protocol deviation for the trial

A protocol deviation is defined as a failure to adhere to the study protocol. Examples are:

- Errors in applying inclusion/exclusion criteria
- The wrong intervention being administered. If this occurs, the site must inform the CRO immediately so that the randomisation block can be adjusted accordingly.
- Patient not wearing the activity tracker at all
- Incorrect/lack of data being collected and documented
- Missed follow-up visits
- Patient is accidentally unblinded.

A protocol deviation should be defined as major or minor. A deviation should be considered to be major if it affects efficacy, the safety, physical or mental integrity of the participants in the trial, or the scientific value of the trial. More details about protocol deviations and a full list are contained in the study protocol.

#### 4.2.3 Description of which protocol deviations will be summarised

The number (and percentage) of patients with major and minor protocol deviations will be summarised by treatment group with details of type of deviation provided. No formal statistical testing will be undertaken on protocol deviations.

#### 4.3 Analysis populations

#### 4.3.1 Definition of analysis populations

Once a patient receives the intervention into which they were randomised, their group is fixed, because this study concerns an implantable device. There are possible protocol deviations, but none that should affect the analysis populations except for the wrong intervention being administered. If this happens, another random patient's intervention should be switched, to avoid unequal sized groups. Therefore the analysis populations will include all randomised patients according to the treatment that they received.

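### After a wrong-implant error the SAP changes a second allocation to keep group sizes equal, departing from the pre-determined order for negligible gain and with no stated mechanism

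*SAP*

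**What the plan says.** Section 3.2 describes "variable block randomisation with block sizes of 4, 6 and 8, with a 1:1 allocation to the 2 groups, with stratification across sites". It is run by the CRO through a validated algorithm in the EDC system. On assignment it says: "Once a patient has been consented, they will be assigned to a treatment group according to the pre-determined order inside the block". The balance it aims for is approximate, not exact: "the numbers in each group will be approximately equal, allowing the interim analyses to take place". On blinding it says: "The surgeon, operating theatre team, radiographic analysts and CRO cannot be blinded".

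Section 4.2.2 lists the wrong intervention as an example of a protocol deviation and says "the site must inform the CRO immediately so that the randomisation block can be adjusted accordingly".

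Section 4.3.1 fixes a patient's group once the randomised implant has been received and names the wrong intervention as the one deviation that should affect the analysis populations. It then says: "If this happens, another random patient's intervention should be switched, to avoid unequal sized groups". It ends with the only population definition in the SAP: "Therefore the analysis populations will include all randomised patients according to the treatment that they received".

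**The concern.** An order that is changed in response to an error report is no longer pre-determined, so sections 4.2.2 and 4.3.1 conflict with section 3.2. The compensating change is also a deliberate act, and four features make it hard to defend.

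- Its direction is known. If a site has implanted one H1 too many, an H1 allocation will become THR, and the site that reported the error can work this out.
- Its mechanism is not stated. The SAP calls the other patient random but does not say who draws, by what method, from which site or block, or whether the EDC system does it.
- It runs through the CRO, which section 3.2 lists as unblinded.
- Nothing downstream would show an effect. In a by-treatment-received population a switched patient counts as an ordinary member of the new arm, and no as-randomised analysis is planned for comparison.

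What is at stake is the protection against selection that random assignment gives the primary H1 versus THR comparison of CCS.

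**Working it through.** **1. What the rule does to allocations.** Because section 4.3.1 fixes the group of a patient already correctly implanted, the switch can reach only (a) a patient assigned but not yet operated on, or (b) an unfilled place in the list. In case (a) a second person receives an implant other than the one allocated. In case (b) no second person does, but a place in the list is now set by the error and not by the original sequence. Either way there are two departures per error: 2/200 = 1% of allocations, against 1/200 = 0.5% without the rule.

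The two sections also describe different actions. Section 4.2.2 adjusts a block, which lies within one site. Section 4.3.1 switches a random patient, with no site named. A draw from another site would balance the overall count but leave both sites unbalanced, although the blocks are stratified by site.

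**2. What equal group sizes are worth.** Inputs from section 3.3: THR success 91%, H1 success 92.7%, margin 8%, type I error 5% (one-sided in the formula), 100 per arm.

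The variance factor is 1/n1 + 1/n2:

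- 100:100 gives 1/100 + 1/100 = 0.020000
- 101:99 gives 1/101 + 1/99 = 0.020002

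Power = Φ[(0.08 + 0.927 − 0.91)/SE − 1.645], with SE² = 0.927 × 0.073/n(H1) + 0.91 × 0.09/n(THR).

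At 100/100, SE² = (0.067671 + 0.0819)/100 = 0.0014957 and SE = 0.03867. Then 0.097/0.03867 = 2.508, less 1.645 = 0.863, and power is 80.6%.

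| Split | Power, more H1 | Power, more THR |
|---|---|---|
| 100/100 | 80.6% | 80.6% |
| 101/99 | 80.6% | 80.6% |
| 105/95 | 80.4% | 80.7% |
| 110/90 | 79.9% | 80.6% |

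One wrong implant costs less than 0.1 percentage point. Five, all in one direction, cost at most about 0.3.

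The SAP's own sample size is 93 per group. With the margin entered as −8 points, its formula and printed rates give 98.3, rounded up to 99. Rounding of the 91% may explain the gap, which is a separate matter. At 93/93 power is 78.1%, and at 94/92 it is 78.0% or 78.1%, so the conclusion here does not depend on it.

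**3. Interim looks.** Section 3.5.1 triggers these at 50 patients per arm. At 51:49 the variance factor is 1/51 + 1/49 = 0.040016, against 0.040000 at 50:50.

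**4. Why an as-randomised analysis needs a companion.** Assume, for illustration only, true rates exactly at the margin: H1 83%, THR 91%, 100 per arm, one-sided 5%. If five THR-allocated patients receive H1, the THR group's expected rate is 0.95 × 0.91 + 0.05 × 0.83 = 0.906. The difference shrinks from −0.080 to −0.076. With SE = √[(0.83 × 0.17 + 0.906 × 0.094)/100] = 0.04757, the type I error is Φ(0.004/0.04757 − 1.645) = 5.9%.

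If five compensating switches are added, the H1 group's expected rate is 0.95 × 0.83 + 0.05 × 0.91 = 0.834 and the difference is −0.072. With SE = 0.04729, the type I error is Φ(0.008/0.04729 − 1.645) = 7.0%.

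Both figures are for analysis by original allocation, which the SAP does not plan. They show that wrong implants dilute such an analysis towards non-inferiority and that compensating switches add to the dilution. They do not measure harm under the SAP's by-treatment-received analysis.

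**The case against.** The best defence rests on the word random. If the second patient is drawn by chance from those not yet operated on, the switched assignment is independent of prognosis. Counted under the implant received, it then adds no expected bias. Section 4.2.2 refers to the protocol for more on deviations, so a mechanism may be described there. Blocks of varying size limit what a site can predict. This stands as far as it goes: a properly concealed draw would do much less harm. It does not rescue the rule. The SAP states the rule itself without the safeguard, the direction of the change is known even if the patient is not, and the gain is negligible however the draw is made.

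A reader might go further and infer the following, which the document does not support:

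- That the randomisation is broken. The rule acts only after a wrong implant, and the SAP gives no expected number of these. With none, nothing changes.
- That allocations are changed by hand, or that a stated concealment is breached. The SAP says neither how the change is made nor, in section 3.2, that the order is concealed. A process of report and then adjustment makes a manual step plausible, no more.
- That the switch moves the CCS difference by about 2 points. That figure comes from counting one failure in THR instead of H1 (about 1/100 in each arm). It is an effect of where the mis-implanted patient is counted, not of switching another patient.

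**Conclusion.** The point holds as a conditional weakness in the plan. The SAP commits in advance to overriding its own allocation order after an error, through an unblinded party, by an unspecified draw, and with no analysis that would reveal the consequence. Each error brings two departures from the sequence in place of one (1% against 0.5% of 200). The resulting bias cannot be sized from the SAP, because neither the number of errors nor the method of the draw is given. What can be sized is the benefit: a change in the variance factor from 0.020002 to 0.020000, and less than 0.1 percentage point of power for one wrong implant. That rests on the success rates, margin and one-sided 5% level of section 3.3 and on a normal approximation. Section 3.2 asks only for approximate balance, so the rule does not serve a need that the design states.

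**What to change.** - In section 4.3.1, delete the sentence on switching another patient's intervention.
- In section 4.2.2, keep the duty to inform the CRO but delete the words on adjusting the block. State that the randomisation list is never altered after an error and that a wrong implant is recorded as a major deviation, with the allocated and the received implant both kept in the data.
- Define an as-randomised population and analyse CCS in it. Place an as-treated or per-protocol analysis alongside, because wrong implants dilute an as-randomised non-inferiority comparison, and say how the two will be read if they disagree.
- Check the protocol for matching wording and align it.

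The cost is a wording change and one further analysis of the primary outcome. Group sizes may differ by one or two patients, with no material loss of power. The change should be made before any such error occurs, because an implant given under the rule cannot be reassigned afterwards.

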## 3 Trial methods

## 3.1 Trial design

The ACTIVE Trial is designed as a randomised (1:1), controlled, assessor- and patient-blinded multicentre non-inferiority trial with two parallel groups and a primary endpoint of composite clinical success 24 months after surgery. The parallel groups will be:

- 1) Experimental: The H1 Implant;
- 2) ACTIVE comparator: cementless total hip replacement (THR).

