## 5.4 Withdrawal/follow-up

The level of consent withdrawal shall be tabulated and classified. Because this study involves implantable devices, patients cannot elect to withdraw from the intervention once it has been administered. Therefore the following types of withdrawal are possible:

- withdraw from the intervention after consent but before surgery;
- withdraw from follow-up but allow data collected to date to be used;
- withdraw from follow-up and withdraw consent for data collected to date to be used;
- lost to contact/follow-up;
- withdraw due to being revised (that is, the device has to be removed);
- patient death.

The classification, timing of and reason for each withdrawal or lost to follow-up shall be tabulated.

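### The SAP's only analysis set groups patients by implant received, with no as-randomised or per-protocol set to support the non-inferiority claim

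*SAP*

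**What the plan says.** The design is a "randomised (1:1), controlled, assessor- and patient-blinded multicentre non-inferiority trial" (SAP 3.1). Allocation happens before surgery: "Once a patient has been consented, they will be assigned to a treatment group according to the pre-determined order inside the block" (SAP 3.2).

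Section 4.3.1 defines the analysis populations:

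- Grouping is by treatment received: "the analysis populations will include all randomised patients according to the treatment that they received".
- For patients who get their allocated device, "Once a patient receives the intervention into which they were randomised, their group is fixed".
- Of the possible protocol deviations, there are "none that should affect the analysis populations except for the wrong intervention being administered".
- When a wrong implant is given, "another random patient's intervention should be switched, to avoid unequal sized groups". Section 4.2.2 likewise has the randomisation block adjusted.

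Section 5.4 lists as one type of withdrawal "withdraw from the intervention after consent but before surgery".

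Table 1 assigns Blackwelder's test to the primary outcome, composite clinical success (CCS), and names no analysis set, so 4.3.1 governs it. The only sensitivity analysis of the primary outcome (section 6.4) concerns missing data above 5% and does not address crossover.

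**The concern.** Randomisation protects the comparison only while patients are compared as they were allocated. Grouping by implant received moves any patient who got the other device into the other arm, and the reason for the move may be related to outcome. In a non-inferiority trial one direction matters most. If H1-randomised patients with poorer prospects receive a THR, the H1 rate rises and the THR rate falls together, and both changes favour the claim.

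A non-inferiority conclusion is normally supported by agreement between an as-randomised and a per-protocol analysis. This SAP has neither, so a reader could not see whether the result depends on who was moved. The set in question decides the trial's primary claim.

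**Working it through.** **1. What the rule does to each kind of patient**

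| Patient | Group under 4.3.1 |
|---|---|
| Randomised to H1, receives H1 | H1 |
| Randomised to H1, receives H1, later revised | Stays in H1 and fails CCS (revision is a failure under 6.1) |
| Randomised to H1, receives a THR at the index operation | THR |
| Randomised, withdraws before surgery | None: randomised, but no treatment received |

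The third row is the possible bias. The fourth is a contradiction in the wording.

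**2. The plan's own threshold**

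Inputs from SAP 3.3: margin 8 points, type I error 5% with z(1−α) in the formula (one-sided, z = 1.645), 100 per arm, THR success 91%. Non-inferiority is declared when the lower bound L is above −8 points:

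L = p_H1 − p_THR − 1.645 × SE, with SE = √[p_H1(1 − p_H1)/n_H1 + p_THR(1 − p_THR)/n_THR]

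For 90/100 v 91/100: SE = √(0.000900 + 0.000819) = 0.0415, and L = −1.0 − 6.8 = −7.8. For 89/100, L = −9.0. The SAP's statement that H1 needs 90% when THR has 91% is reproduced.

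**3. An example in which the conclusion changes (assumed counts)**

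- As randomised, H1 88/100 v THR 91/100: difference −3.0, SE = √(0.001056 + 0.000819) = 0.0433, L = −3.0 − 7.1 = −10.1. Non-inferiority is not shown.
- Suppose 3 of the H1-randomised patients received a THR, of whom 2 failed and 1 succeeded. As treated, H1 is (88 − 1)/(100 − 3) = 87/97 = 89.7% and THR is (91 + 1)/(100 + 3) = 92/103 = 89.3%. The difference is +0.4, SE = 0.0434, L = −6.8. Non-inferiority is declared from the same patients and outcomes.

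The switching rule would restore equal arms but need not restore the answer. If 3 THR-randomised patients were switched to H1 and all succeeded, the result is 90/100 v 89/100, L = +1.0 − 7.1 = −6.1, still declared. If one of the 3 failed, it is 89/100 v 90/100, L = −1.0 − 7.1 = −8.1, narrowly not declared.

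**4. Type I error at the margin**

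Assumptions: true as-randomised success 83% (H1) v 91% (THR), 100 per arm, one-sided 5%. Of the H1-randomised patients, x receive a THR and succeed at rate s. To keep the as-randomised H1 rate at 83%, the others succeed at (83 − x·s)/(100 − x). The THR-treated group has expected rate (91 + x·s)/(100 + x). For x = 5 and s = 50%: 80.5/95 = 84.7% v 93.5/105 = 89.0%, a difference of −4.3 instead of −8.0.

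| x | s | Expected as-treated difference (points) | Type I error, as treated |
|---|---|---|---|
| 5 | 91% | −8.4 | 4.7% |
| 5 | 83% | −7.6 | 6.6% |
| 5 | 70% | −6.3 | 10.7% |
| 5 | 50% | −4.3 | 20.1% |
| 3 | 50% | −5.8 | 12.6% |
| 2 | 50% | −6.5 | 9.5% |

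The as-randomised analysis gives 5.2% to 5.4% in these scenarios. Dropping the crossed-over patients instead of moving them still gives about 11% at x = 5, s = 50%, so a per-protocol set alone would not cure the problem.

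**The case against.** Four counter-arguments deserve weight.

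- **Crossover need not be prognostic.** The SAP speaks only of a wrong intervention being given. It does not mention a change of implant decided during surgery, and a mix-up need not relate to prognosis. This stands. A reader might infer that the rule is bound to favour H1, but the documents do not support that. At 91% success among crossovers the error is 4.7%, slightly below the as-randomised figure. Crossover from THR to H1 by patients who do badly would count against H1.
- **Implants are permanent.** Grouping by device is natural for adverse device effects and implant survival. That is right for those outcomes, but does not justify it for the primary comparison.
- **Revisions are not moved.** A reader might infer that an H1 later revised to a THR counts as control. Section 4.3.1 fixes the group once the allocated device is received, and 6.1 counts the revision as a failure. The point is confined to the index operation.
- **The example depends on the counts and the level.** At the SAP's own 90/100 v 91/100 the nominal margin is already met, so moving H1 failures into THR changes no conclusion there. The example above uses the one-sided 5% of section 3.3. With the two-sided 95% interval of section 4.1.4 (z = 1.96), its as-treated bound is 0.4 − 8.5 = −8.1, which is not a pass. If all 3 crossovers failed, 88/97 v 91/103 gives 2.4 − 8.5 = −6.1, which is.

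Nor does the SAP say outright that patients withdrawn before surgery are excluded. It reports them, but gives them no group.

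**Conclusion.** The concern holds in a conditional form. What is certain is the text: one as-treated set governs a non-inferiority primary endpoint, the SAP offers no other set, and the rule cannot be applied to patients who were randomised but never operated on. The direction and size of any bias are not certain. With no crossover, the rule does no harm among operated patients. With 5 H1-to-THR crossovers per 100, the type I error ranges from 4.7% to 20.1% as their assumed success falls from 91% to 50%, and 2 crossovers at 50% already give 9.5%. The crossover numbers and success rates are assumptions, because the SAP supplies neither.

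The rule should be changed before analysis. Error control for the primary claim should not depend on why patients received the other implant, and the change is cheap.

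**What to change.** Rewrite section 4.3.1 as follows and name the set for each row of Table 1:

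1. **Primary set:** all randomised patients, analysed in the arm to which they were randomised. State how those never operated on are handled, since CCS is defined 24 months after surgery. One option is to cover them in the missing-data analysis of section 6.4, which as written starts only above 5% missing.
2. **Per-protocol set:** patients who received the randomised implant and had no major deviation. Require a result consistent with the primary set before non-inferiority is claimed.
3. **As-treated set:** for adverse events and implant survival only.
4. **Remove the switching rule** in 4.3.1 and the matching block adjustment in 4.2.2. Slightly unequal arms are harmless, whereas switching breaks a second patient's randomisation. If the rule stayed, the new as-randomised set would contain patients deliberately given the other device, which dilutes any true difference and so favours non-inferiority.

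The cost is SAP wording, one extra run of the primary analysis and slightly unequal arm sizes. No new data are needed.
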